9.1 Subject completion

A subject who returns for the concluding visit/is available for the concluding contact foreseen in the protocol is considered to have completed the study.

9.2 Subject withdrawal

Subjects who are withdrawn for AEs must be clearly distinguished from subjects who are withdrawn for other reasons. Investigators will follow subjects who are withdrawn as result of a SAE/AE until resolution of the event (see Section 8.7).

Withdrawals will not be replaced.

9.2.1 Subject withdrawal from the study

From an analysis perspective, a 'withdrawal' from the study is any subject who did not come back for the concluding visit foreseen in the protocol.

A subject qualifies as a 'withdrawal' from the study when no study procedure has occurred, no follow-up has been performed and no further information has been collected for this subject from the date of withdrawal/last contact.

Investigators will make an attempt to contact those subjects who do not return for scheduled visits or follow-up.

Information relative to the withdrawal will be documented on the Study Conclusion page of the CRF. It will be specified which of the following possible reasons were responsible for withdrawal:

- serious adverse event
- non-serious adverse event
- protocol violation (specify)
- consent withdrawal, not due to an adverse event
- moved from the study area
- lost to follow-up
- other (specify)

9.2.2 Subject withdrawal from investigational product

A 'withdrawal' from the investigational product is any subject who does not receive the complete treatment, i.e. when no further planned dose is administered from the date of withdrawal. A subject withdrawn from the investigational product may not necessarily be withdrawn from the study as further study procedures or follow-up may be performed (safety or immunogenicity) if planned in the study protocol.

Information relative to premature discontinuation of the investigational product will be documented on the Vaccine Administration page of the CRF. The investigator will document whether the decision to discontinue further vaccination was made by the the subject's parent or guardian or the investigator and which of the following possible reasons was responsible for withdrawal:

- serious adverse event,
- non-serious adverse event,
- other (specify).

9.3 Extension study

There will be a retrospective follow-up of SAE(s) that occurred since the last study visit [Visit 7] up to the time that subjects are at least 24 months of age.

(Amendment 7: 12 April 2006)

9.4 Screen and baseline failures

Not applicable.

10 Data Evaluation: Criteria for Evaluation of Objectives

Note: Data collected for the ancillary study will be provided to the investigators of the ancillary study for evaluation (refer to Appendix H and Section 5.2).

10.1 Co-primary endpoints

Immunogenicity: post-primary vaccination

In all subjects, one month after the 3rd dose of the primary vaccination:

- Serum bactericidal antibody titer (MenC) $\geq 1:8$ (seropositivity)
- Serum bactericidal antibody titer (MenA) $\geq 1:8$ (seropositivity)
- Anti-PRP concentration $\geq 1 \mu\text{g/ml}$ (seroprotection)
- Anti-HBs concentration $\geq 10 \text{ mIU/ml}$ (seroprotection)
- Anti-tetanus concentration $\geq 0.1 \text{ IU/ml}$ (seroprotection)
- Anti-diphtheria concentration $\geq 0.1 \text{ IU/ml}$ by ELISA and, if negative, $\geq 0.016 \text{ IU/ml}$ by Vero-cell (seroprotection)
- Concentration of anti-BP antibodies

10.2 Secondary endpoints

Immunogenicity

Pre-primary vaccination

In all subjects, just prior to the administration of the 1st dose of the primary vaccination

- SBA-MenA titer $\geq 1:8$ (seropositivity)
- SBA-MenC titer $\geq 1:8$ (seropositivity)
- Anti-PSA concentration $\geq 0.3 \mu\text{g/ml}$ (seropositivity)
- Anti-PSC concentration $\geq 0.3 \mu\text{g/ml}$ (seropositivity)
- Anti-PSA concentration $\geq 2 \mu\text{g/ml}$
- Anti-PSC concentration $\geq 2 \mu\text{g/ml}$
- Anti-diphtheria concentration $\geq 0.1 \text{ IU/ml}$ (seroprotection)
- Anti-HBs concentration $\geq 10 \text{ mIU/ml}$ (seroprotection)
- Anti-BP concentration $\geq 15 \text{ EL.U/ml}$ (seropositivity)
- Concentration/titers of SBA-MenA, SBA-MenC, anti-PSA, anti-PSC, anti-HBs, anti-diphtheria and anti-BP antibodies

Post-primary vaccination:

In all subjects, one month after the 3rd dose of the primary vaccination:

- Anti-PSA concentration $\geq 0.3 \mu\text{g/ml}$ (seropositivity)
- Anti-PSC concentration $\geq 0.3 \mu\text{g/ml}$ (seropositivity)
- Anti-PSA concentration $\geq 2 \mu\text{g/ml}$
- Anti-PSC concentration $\geq 2 \mu\text{g/ml}$
- Anti-PRP concentration $\geq 0.15 \mu\text{g/ml}$ (seroprotection)
- Anti-BP concentration $\geq 15 \text{ EL.U/ml}$

Titers/Concentrations of all antibodies but anti-BP (see co-primary endpoints)

Antibody persistence:

In all subjects, at twelve months of age, just prior to the administration of 1/5 of a dose of MencevaxTM AC:

- SBA-MenA titer $\geq 1:8$ (seropositivity)
- SBA-MenC titer $\geq 1:8$ (seropositivity)
- Anti-PSA concentration $\geq 0.3 \mu\text{g/ml}$ (seropositivity)
- Anti-PSC concentration $\geq 0.3 \mu\text{g/ml}$ (seropositivity)
- Anti-PSA concentration $\geq 2 \mu\text{g/ml}$
- Anti-PSC concentration $\geq 2 \mu\text{g/ml}$
- Anti-PRP concentration $\geq 0.15 \mu\text{g/ml}$ (seroprotection)
- Anti-PRP concentration $\geq 1 \mu\text{g/ml}$ (seroprotection)
- Anti-HBs concentration $\geq 10 \text{ mIU/ml}$ (seroprotection)
- Anti-tetanus concentration $\geq 0.1 \text{ IU/ml}$ (seroprotection)
- Anti-diphtheria concentration $\geq 0.1 \text{ IU/ml}$ by ELISA and, if negative, $\geq 0.016 \text{ IU/ml}$ by Vero-cell (seroprotection)
- Anti-BP concentration $\geq 15 \text{ EL.U/ml}$ (seropositivity)
- Concentration/titers of SBA-MenA, SBA-MenC, anti-PSA, anti-PSC, anti-PRP, anti-HBs, anti-tetanus, anti-diphtheria and anti-BP antibodies.

Immune memory:

In all subjects, one month after the administration of 1/5 of a dose of MencevaxTM AC:

- SBA-MenA titer $\geq 1:8$ (seropositivity)
- SBA-MenC titer $\geq 1:8$ (seropositivity)
- Anti-PSA concentration $\geq 0.3 \mu\text{g/ml}$ (seropositivity)
- Anti-PSC concentration $\geq 0.3 \mu\text{g/ml}$ (seropositivity)
- Anti-PSA concentration $\geq 2 \mu\text{g/ml}$
- Anti-PSC concentration $\geq 2 \mu\text{g/ml}$
- Concentration/titers of SBA-MenA, SBA-MenC, anti-PSA and anti-PSC antibodies.

Reactogenicity and safety:

After each vaccine dose:

- Occurrence of solicited symptoms (during the 4-day follow-up period)
Local: Pain and swelling at the injection site
General: Drowsiness, Fever, Irritability/ Fussiness, Loss of appetite
- Occurrence of unsolicited symptoms (during the 30-day follow-up period)

Over the full course of the study:

- Occurrence of serious adverse events

10.3 Estimated sample size

The target sample size is 280 enrolled subjects to reach 220 evaluable subjects in the ATP cohort for immunogenicity (110 evaluable subjects in each group). Refer to Section 10.4 for definition of study cohorts.

The co-primary objectives of the study are:

One month after primary vaccination:

- To demonstrate the immunogenicity of Tritanrix™-HepB/Hib-MenAC with respect to SBA-MenA and SBA-MenC.
- To demonstrate that Tritanrix™-HepB/Hib-MenAC is non-inferior to the control vaccine Tritanrix™-HepB/ Hiberix™ with respect to the immunogenicity of all common antigens (anti-PRP, anti-Diphtheria, anti-Tetanus, anti-BP, and anti-HBs).

Criteria to achieve the co-primary objectives:

1. Immunogenicity of SBA-MenA and SBA-MenC: lower limit of the 95% CI for the percentage of subjects with SBA-MenA titers (respectively SBA-MenC titers) $\geq 1:8$ is greater than 80%.
2. Non-inferiority for all common antigens: upper limit of the 95% CI for the group difference in terms of the percentage of subjects with anti-PRP concentration $\geq 1 \mu\text{g/ml}$ (respectively, anti-diphtheria concentration $\geq 0.1 \text{ IU/ml}$, anti-tetanus concentration $\geq 0.1 \text{ IU/ml}$, anti-HBs concentration $\geq 10 \text{ mIU/ml}$) is below 10% and upper limit of the 95% CI for the group GMC ratio in anti-BP is below 1.5.

In order to cope with the multiplicity of the objectives, the criteria of the objectives will be assessed sequentially and will lead to a conclusion only if all previous primary criteria have been met (refer to Section 10.6.2). **Table 10-1** and **Table 10-2** present the order in which the criteria will be assessed (see Rank), the power to meet each criterion and the power to meet all previous criteria (see cumulative power). For instance, the power to meet the first primary objective and non-inferiority for anti-PRP will be 78.6% assuming that the 2 vaccine groups are identical with respect to the primary endpoints.

Table 10-1: Power for criterion 1 (one-sided test on one proportion, $\alpha=0.025$, $N=110$ /group, power for $H_0: p = 80\%$ under the alternative hypothesis $H_a: p = 94\%$, power calculated using PASS 2000)

Rank	Endpoint	Reference	Individual Power	Cumulative power
1	SBA Men C = 1:8	94%	99.4%	99.4%
2	SBA Men A = 1:8	94%	99.4%	98.8%

Reference: MenAC-Hib-001

Table 10-2: Power for criterion 2 (For all antigens except anti-BP: one-sided test of equivalence of two proportions, $\alpha=0.025$, $N=110$ /group, power calculated using PASS 2000, assuming identical seroprotection rates for the two groups; for anti-BP: one-sided t-test of equivalence of two means, $\alpha = 0.025$, $N = 110$ /group, power calculated using nQuery 4 and assuming identical GMCs for the two groups.)

Rank	Endpoint	Reference	Individual Power	Cumulative power
3	Anti-PRP = 1 µg/ml	94%	79.8%	78.6%
4	Anti-tetanus = 0.1 IU/ml	98%	97.9%	76.5%
5	Anti-Diphtheria = 0.1 IU/ml by ELISA and, if negative, ≥ 0.016 IU/ml by Vero-cell	96%	89.1%	65.6%
6	GMC of anti-BP	0.298*	99.0%	64.9%
7	Anti-HBs = 10 mIU/ml	95%	84.4%	49.0%

*standard deviation of log₁₀ (concentration)

References: MenAC-Hib-001 for % of anti-PRP, Hib-065 for % of anti-tetanus, anti-diphtheria (by ELISA only) and anti-HBs, DTPw-HBV-033 for s.d. of log₁₀ (concentration) for anti-BP.

It is acknowledged that the power to meet all primary objectives is low (at worst 49.0%). However, considering this is a Phase II feasibility study, the low power is deemed acceptable.

10.4 Study cohorts to be evaluated

A total of 6 cohorts are defined for the purpose of analysis.

- Three cohorts that will be used for the analysis of the primary vaccination course:
 - the Total vaccinated cohort
 - the ATP cohort for safety
 - the ATP cohort for immunogenicity (used for the analysis of the co-primary objectives of immunogenicity)
- Three cohorts that will be used for the analysis of the booster phase:
 - the Total vaccinated cohort

- the ATP cohort for safety
- the ATP cohort for immune memory

The Total vaccinated cohort (Primary vaccination)

The Total vaccinated cohort will include all subjects vaccinated in the primary phase of the study. For the Total analysis of safety, this will include all subjects vaccinated in the primary phase of the study with at least one vaccine administration documented in the primary phase. For the Total analysis of immunogenicity / efficacy, this will include subjects vaccinated in the primary phase of the study for whom data concerning immunogenicity/efficacy endpoint measures are available. The Total vaccinated cohort analysis will be performed per treatment actually administered.

According to protocol (ATP) cohort for safety (Primary vaccination)

The According to protocol (ATP) cohort for safety will include all subjects:

- who have received at least one dose of study vaccine/control according to their random assignment,
 - with sufficient data to perform an analysis of safety,
 - for whom the administration route of study vaccine/control is known and correct,
 - who have not received a vaccine not specified or forbidden in the protocol,
 - who did not receive a replacement vaccine,
- during the primary vaccination course.

According to protocol (ATP) cohort for immunogenicity (Primary vaccination)

The According to protocol (ATP) cohort for immunogenicity will include all evaluable subjects (i.e. those meeting all eligibility criteria, complying with the procedures defined in the protocol, and with no elimination criteria during the study) from the ATP cohort for safety for whom assay results are available for antibodies against at least one study vaccine antigen component at Visit 4.

The Total vaccinated cohort (Booster vaccination)

The Total vaccinated cohort will include all subjects vaccinated in the booster phase of the study. For the Total analysis of safety, this will include all subjects vaccinated in the booster phase of the study with at least one vaccine administration documented in the booster phase. For the Total analysis of immunogenicity/efficacy, this will include subjects vaccinated in the booster phase of the study for whom data concerning immunogenicity / efficacy endpoint measures are available. The Total vaccinated cohort analysis will be performed per treatment actually administered.

According To Protocol (ATP) cohort for safety (Booster vaccination)

The ATP cohort for safety will include all subjects from the ATP cohort (Primary vaccination) for safety

- who have received the 3 doses in the primary vaccination course,
- who have received the booster dose,
- with documented safety follow-up,
- for whom administration route of Mencevax™ AC is known,
- who have not received a vaccine not specified or forbidden in the protocol.

This cohort will also be used for the analysis of persistence of the immune response.

According To Protocol (ATP) cohort for immune memory

The ATP cohort for immune memory will include all evaluable subjects (i.e., those meeting all eligibility criteria, complying with the procedures defined in the protocol, with no elimination criteria during the study) from the Booster ATP cohort for safety for whom assay results are available for antibodies against at least one study vaccine antigen component at Visit 7.

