4.4 Elimination criteria during the study

The following criteria should be checked at each visit subsequent to the first visit. If any become applicable during the study, it will not require withdrawal of the subject from the study but does determine a subject's evaluability in the according-to-protocol (ATP) analysis. See Section 10.4 for definition of study cohorts to be evaluated.

- Use of any investigational or non-registered drug or vaccine other than the study vaccine(s) during the study period.
- Chronic administration (defined as more than 14 days) of immunosuppressants or other immune-modifying drugs during the study period. (For corticosteroids, this will mean prednisone, or equivalent, ≥ 0.5 mg/kg/day. Inhaled and topical steroids are allowed).
- Administration of a vaccine not foreseen by the study protocol during the period starting from **30 days** before the first dose of vaccine(s) and ending 30 days after the last dose of vaccine(s) with the exception of OPV.
- Administration of a meningococcal vaccine not foreseen by the study protocol during the entire study period.
- Administration of immunoglobulins and/or any blood products during the study period.

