10.7 Final Analyses for the booster vaccination

10.7.1 Analysis of immunogenicity

The analysis of antibody persistence and the analysis of immune memory will be respectively based on the ATP cohort for safety and the ATP cohort for immune memory. If, for any vaccine group, the percentage of enrolled subjects with serological results excluded from an ATP cohort is more than 5%, a second analysis based on the Total vaccinated cohort will be performed to complement the ATP analysis.

The analysis of immunogenicity will be as follows:

Analysis of antibody persistence

For each treatment group, one month after the third dose of the primary vaccination course and just before the administration of one fifth of a dose of Mencevax™ AC:

- Geometric Mean antibody Concentrations/Titers (GMCs/GMTs) with 95% confidence intervals (CIs) will be tabulated for each antibody. Calculation of the

GMCs/GMTs is performed by taking the anti-log of the mean of the log concentration/titer transformations.

- Seropositivity / seroprotection rates with exact 95% CIs will be calculated.
- Antibody concentrations/titers pre-booster will also be investigated using reverse cumulative curves for each antigen and serotype.

Analysis of immune memory

For each treatment group, just before and one month after the administration of one fifth of a dose of MencevaxTM AC:

- Geometric Mean antibody Concentrations/Titers (GMCs/GMTs) with 95% confidence intervals (CIs) will be tabulated for each antibody. Calculation of the GMCs/GMTs is performed by taking the anti-log of the mean of the log concentration/titer transformations.
- Seropositivity / seroprotection rates with exact 95% CIs will be calculated.
- Antibody concentrations/titers post-booster will also be investigated using reverse cumulative curves for each antigen and serotype.

The ratio of the GMCs/GMTs between the TritanrixTM-HepB/Hib-MenAC group and the TritanrixTM-HepB/HiberixTM group one month after the administration of one fifth of a dose of MencevaxTM AC, will be computed with its 95% CI. The ratio and its 95% CI will be computed using an ANOVA model on the log-transformed concentration/titer with group effect as regressor.

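### Antibody persistence at 12 months is analysed on a safety cohort that skips most ATP evaluability rules and sets conditions arising after the blood sample

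*Protocol*

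**What the plan says.** After listing the conditions for the booster-phase ATP cohort for safety, Section 10.4 adds: "This cohort will also be used for the analysis of persistence of the immune response". Section 10.7.1 agrees: persistence and immune memory "will be respectively based on the ATP cohort for safety and the ATP cohort for immune memory".

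The cohort starts from the primary-phase ATP cohort for safety and requires all three primary doses. Its booster-phase conditions include "who have received the booster dose", "with documented safety follow-up" and "for whom administration route of Mencevax™ AC is known". It also excludes anyone given an unspecified or forbidden vaccine.

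Section 10.2 times the persistence endpoints "In all subjects, at twelve months of age, just prior to the administration of 1/5 of a dose of" Mencevax AC, which is the Visit 6 draw. Section 4.4 lists the elimination criteria, among them "Administration of immunoglobulins and/or any blood products during the study period". It states that they decide a subject's evaluability in the ATP analysis and points to Section 10.4 for the cohorts. Section 5.3 says the same of the intervals between visits.

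**The concern.** A persistence cohort should hold infants whose Visit 6 antibody reflects the primary course, and should be fixed by what is known up to that draw. The chosen cohort departs from this in two ways.

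First, it keeps infants whom the protocol elsewhere treats as non-evaluable. Donor antibody could raise a Visit 6 result and chronic immunosuppression could lower one. Section 1.4 names malaria and anaemia among the top causes of death at the district hospital, so exposure to blood products is plausible, though no rate is given.

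Second, it can remove infants for events after a valid sample was drawn. At stake is the secondary objective on persistence to all antigens at 12 months.

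**Working it through.** The protocol states no figure for the persistence analysis, so there is nothing to reproduce. The check is a comparison of the definitions in Section 10.4, followed by arithmetic for scale.

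| Rule | Primary ATP immunogenicity | Booster ATP safety (used for persistence) | ATP immune memory |
|---|---|---|---|
| Eligibility and compliance with procedures | yes | no | yes |
| Section 4.4: blood products, immunosuppressants, investigational drugs | yes | no | yes |
| Unspecified or forbidden vaccine | yes | yes, with no cut-off at Visit 6 | yes |
| Challenge dose received, route known, follow-up documented | not applicable | yes | yes |
| Assay result required | Visit 4 | none | Visit 7 |

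**Retention.** The primary ATP cohort for safety, from which the booster cohort is drawn, does not apply the middle group of Section 4.4 criteria either. An infant transfused before Visit 6, or bled outside the 11 to 13 month window, therefore stays in.

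**Exclusion.** Section 5.4 lists the Visit 6 blood collection before the contraindication check and the challenge. An infant who is bled and then not challenged has a 12-month result but leaves the cohort. A forbidden vaccine given between Visits 6 and 7 has the same effect.

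**Internal mismatch.** Section 10.7.1 tabulates Visit 6 MenA and MenC results twice: once for persistence, and once as the pre-challenge values for memory, where elimination criteria apply. It also tabulates the post-dose-3 results again, which Section 10.6.2 reports on the ATP immunogenicity cohort. Two ATP values for the same time point can differ solely through cohort rules.

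**Scale of retention.** Assume n = 110 per group (the evaluable number in Section 10.3; none is stated for persistence), and k infants with passive antibody, all counted as positive. With true rate p, the upward shift is k(1 − p)/n:
- p = 50%: 1 × 0.5/110 = 0.5 points; 5 × 0.5/110 = 2.3 points
- p = 70%: 0.3 to 1.4 points
- p = 90%: 0.1 to 0.5 points
- p = 5% (for example, an unprimed control group): 0.9 to 4.3 points

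If these infants' levels are R times the group's, the GMC is multiplied by R^(k/n). R = 10 gives 1.02 to 1.11 and R = 100 gives 1.04 to 1.23. Both k and R are assumptions.

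**Scale of exclusion.** If a share s of infants with a Visit 6 result is dropped, the rate shifts by s × (rate in those kept − rate in those dropped). The second analysis runs when more than 5% of subjects with serology are excluded in any group, that is 6 of 110 or 8 of 140. Below that trigger, s is at most about 5%. The shift then cannot exceed about 5 points, and is far less unless the dropped infants differ sharply. Infants wrongly kept never count toward the trigger.

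**The case against.** **The cohort is not free of elimination rules.** It bars unspecified and forbidden vaccines, which covers the unforeseen-vaccine criteria of Section 4.4, including an unplanned meningococcal vaccine. Planned immunoglobulin or blood products are already an enrolment exclusion. This stands and narrows the gap to the remaining criteria, eligibility and the intervals.

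**Section 4.4, Section 5.3 and the glossary could be read as governing every ATP analysis.** An analyst might apply them here. But Section 4.4 sends the reader to Section 10.4, which applies the criteria to two ATP cohorts and omits them from the safety cohorts. On this reading the sections conflict and still need reconciling.

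**Losses after the sample are few.** The draw and challenge fall in the same visit. Home visits on days 0 to 3 may satisfy the follow-up condition, since Visit 7 is not named. The 5% rule caps unexamined loss. This largely stands.

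**The complementary analysis covers it.** A reader might infer the opposite, that the booster Total vaccinated cohort also drops unchallenged infants. The text does not settle that. Table 5-1 places the Visit 5 measles and yellow fever vaccination in the booster phase; if it counts, such infants remain. Either way the analysis is conditional and does not remove blood-product recipients.

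**The bias is speculative.** A reader might infer that persistence will be overstated by a known amount. The documents do not support that: they give no exposure rate, the shifts above assume every recipient turns positive, and retained immunosuppressed infants would pull the other way. At p = 70% the shift is well within the approximate 95% half-width, 1.96 × √(0.7 × 0.3/110) = 8.6 points. At p = 5% the five-infant extreme of 4.3 points is about as large as the half-width, 1.96 × √(0.05 × 0.95/110) = 4.1 points, but only on that extreme assumption.

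**Conclusion.** The concern holds as a cohort-definition fault. Both sections that address persistence assign it to a cohort that omits most of the protocol's own ATP evaluability rules and sets conditions arising after the sample. The protocol fixes this choice explicitly, so it is not a detail left for the SAP.

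The size and net direction of the effect are unknown; the effect is probably small. The conclusion rests on the definitions, not on the illustrative shifts, whose exposure counts and antibody levels are assumed.

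A reader might also infer that the co-primary or immune-memory results are compromised. They are not. The co-primary analysis uses the ATP cohort for immunogenicity, and the memory cohort applies the elimination criteria. Persistence is reported only as GMCs/GMTs, rates and reverse cumulative curves by group, with no test or margin. The change is worth making because it costs little, but no confirmatory conclusion depends on it.

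**What to change.** In Section 10.4, remove the sentence that assigns persistence to the safety cohort and define an ATP cohort for persistence. It would comprise infants who:
- met the eligibility criteria;
- received three primary doses as randomised;
- had no Section 4.4 elimination criterion up to the Visit 6 draw;
- had Visit 6 within the 11 to 13 month window;
- have at least one Visit 6 assay result.

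Set no condition on a Visit 4 assay result, on receipt or route of the challenge dose, or on later follow-up. For that reason the cohort should not be built from the primary ATP cohort for immunogenicity: that cohort requires a Visit 4 result and would drop valid Visit 6 samples for an unrelated reason.

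Name the new cohort in Section 10.7.1 for persistence, with all available Visit 6 results as the complementary analysis in place of the booster Total vaccinated cohort.

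The cost is one definition and one matching edit. Blood products, immunosuppressants and investigational products are already recorded under Section 6.8, and visit dates and assay results are already collected.
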